8.3.2 Secondary

1. PK parameters: C_{max} , AUC, V_d and CL of APR-246, and C_{max} , time to maximum concentration (T_{max}), and AUC of venetoclax.
2. PD analysis of circulating peripheral blood cells to determine effects of APR-246 on cellular viability and apoptosis (*PK/PD Substudy of APR-246 Monotherapy*).
3. PK parameters after oral dosing: C_{max} , T_{max} , AUC, relative bioavailability (F), apparent volume of distribution (V_d/F) and apparent clearance (CL/F) of APR-246, (*PK/PD Substudy of APR-246 Monotherapy*).
4. CR rate, defined as the proportion of patients who achieve CR as per response criteria.
5. ORR, defined as the proportion of patients achieving a response, as per response criteria.
6. DOR, defined as the time from documentation of tumor response to disease progression or death as a result of any cause.
7. PFS, defined as the time from the first study dose date to the date of first documentation of confirmed disease progression or death (whichever occurs first).

8.3.3 Exploratory

The exposure response relationship for safety and efficacy of APR-246 when combined with venetoclax and rituximab therapy.

8.4 Safety Stopping Criteria

The study will implement the following stopping criteria:

- Any death occurring between receipt of the first dose of APR-246 through 30 days of last dose of study treatment which is not clearly and solely due to underlying disease.
- A medically equivalent SAE experienced by >1 patient, which is not clearly and solely due to underlying disease.
- A severe AE (NCI-CTCAE toxicity grade >3) experienced by >2 patients that does not return to grade ≤1 or baseline within 7 days.
- A grade ≥3 neurologic AE that does not return to grade ≤1 or baseline within 7 days.

If a stopping criterion is met, enrollment will be temporarily suspended. The DRT will perform a prompt cumulative review of safety data and the circumstances of the event(s) in question to determine whether dosing and/or the protocol should be modified.

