	
APR-246 PO on Day 2. The primary purpose of the monotherapy cycle is to obtain peripheral blood for monotherapy PK and PD analyses following IV and PO administration of APR-246.
 
Patients will start treatment with APR-246 IV as a single agent administered on Day 1 of a single 7-day monotherapy cycle at the assigned cohort dose level, prior to Cycle 1 Day 1 of combination therapy. On Day 2 of the 7-day monotherapy lead-in period, patients will receive a single dose of APR-246 administered PO at the dose of 500 mg. After review of oral PK data from at least 6 patients, a decision can be made whether to increase the PO dose of APR-246 and/or administer APR-246 with a standard high-fat meal to investigate, respectively, dose linearity in PK and/or the effect of food on oral absorption of APR-246. Dose escalation of the oral dose or switching to administration with food will be determined by PK to ensure that the APR-246 exposure levels after oral dosing do not exceed the exposure levels after IV administration in terms of C_{max} and AUC.
 
Combination Treatment
 
After the APR-246 monotherapy lead-in, study treatment will consist of APR-246 administered as an IV infusion, at the same assigned dose that was used during the monotherapy lead-in period, once weekly, on Days 1, 8 and 15 of each cycle, concurrently with venetoclax for the 5-week ramp-up at the dose of 20 mg during Week 1, 50 mg during Week 2, 100 mg during Week 3, 200 mg during Week 4, and 400 mg during Week 5. Beginning Cycle 2 Day 1, venetoclax will be administered at 400 mg (or tolerable dose following 5-week ramp up) PO daily. IV rituximab will be initiated at 375 mg/m² on Cycle 2, Day 2 and then administered at 500 mg/m² on Day 2 of Cycles 3-7. After 6 cycles of treatment with APR-246 in combination with venetoclax + rituximab, APR-246 + venetoclax will continue to be administered starting at Cycle 8 for up to a total of 24 cycles. The safety assessment (DLT) period will occur in the monotherapy lead-in and throughout Cycles 1, 2, and 3 of combination treatment.
 
Patients with RT will receive APR-246 administered IV as the assigned cohort dose with standard doses of venetoclax and rituximab. Dose escalation will proceed in a standard 3 + 3 dose escalation design.
 
Patients who miss >25% of APR-246 doses for a nonmedical reason (patient's preference) or noncompliance will be replaced.
 
Patients who receive at least 3 cycles of study treatment at the assigned dose of APR-246 may proceed to the next dose level of APR-246 that has been demonstrated as safe and tolerable by the DRT in at least 3 patients, provided the dose increase is considered to be in the patient's best interest by the Investigator.
 
Responses will be assessed according to response criteria for RT (Appendix V) via blood, BM, and imaging (positron emission tomography [PET]/computed tomography [CT]). Response assessments are to be performed every 3 cycles and PET-CT scanning is recommended. For patients who achieve CR, imaging may be omitted, and minimal residual disease (MRD) assessment will be completed using flow cytometry and/or molecular techniques from the BM and/or peripheral blood.

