--	--

	
If a stopping criterion is met, enrollment will be temporarily suspended until the DRT has performed a prompt cumulative review of safety data and the circumstances of the event(s) in question, to determine whether dosing and/or the protocol should be modified.
 
Determination of Sample Size
 
This trial assumes a sample size of up to 48 patients in total, with up to 6 patients in each of the 3 cohorts and an additional 10 patients added at the MTD, or maximum tolerated dose, to gain further confidence in the recommended dose of APR-246. If Dose Level 3 is determined to be the MTD, up to 10 additional patients may be added and treated at both Dose Levels 1 and 2 to obtain additional safety, PK, and/or PD information. No sample size and power calculations are performed for this phase 1 study.
 
Patients who miss >25% of APR-246 doses for a nonmedical reason (patient's preference) or noncompliance in the safety lead-in cohorts will be replaced.
 
Recommended Dose
 
The recommended dose of APR-246 in combination with venetoclax and rituximab represents the dose of APR-246 at or below the maximum tested dose, or the MTD, that results in the greatest apoptosis of circulating malignant cells in the monotherapy cycle.
 
Analysis Populations
 
Safety population: Patients will be evaluable for safety if they receive at least one dose of APR-246. The safety population will be the primary analysis population used for all analyses such as patient disposition, patient demographics, exposure, safety parameters and efficacy parameters. The safety population will be the primary analysis population for efficacy.
 
Efficacy evaluable (EE) population: All patients who complete at least one treatment cycle of APR-246 and venetoclax and rituximab and who have at least one post-treatment clinical response assessment. The EE population will be the secondary analysis population for efficacy.
 
PD population: Patients will be evaluable for PD if at least one sample for PD evaluation has been obtained after administration of APR-246.
 
PK population: Patients will be evaluable for PK if at least one sample for PK evaluation has been obtained.
 
Efficacy Analyses
 
CR rate will be summarized for the safety and EE patients as the proportion (%) of patients with CR. In addition to presenting the CR rate, its associated exact 95% confidence intervals (CI) will also be presented.
 
DOR is defined as the time from the date when criteria for response are met to the date of disease progression or death due to any cause, whichever occurs first. Patients alive with no disease progression will have their DOR censored at the date of the last clinical assessment. The duration of CR will be summarized by providing the median DOR together with associated 95% CI, using Kaplan-Meier methodology.
 
ORR will be summarized in number (%) of patients in each category of responses and ORR will be analyzed by using a similar method to the one used for the CR rate. ORR is defined as the number of patients who achieve CR and partial remission.

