Upon determination of the pharmacologically active dose or MTD, or when the maximally intended dose is reached, up to 10 additional patients may be enrolled at this dose level to confirm the assessment and to collect additional safety, PK and PD data to aid in determining the recommended dose of APR-246 in combination with venetoclax and rituximab.

Table 3. APR-246 Dose Levels

Dose Modification	APR-246 Dose
Dose Level 1	APR-246 1.5 g/day 0.5 g (for first 45 minutes) + 1.0 g (for 5 hours 15 minutes)
Dose Level 2	APR-246 3.0 g/day 1.0 g (for first 45 minutes) + 2.0 g (for 5 hours 15 minutes)
Dose Level 3	APR-246 4.0 g/day 1.33 g (for the first 45 minutes) + 2.66 g (for 5 hours 15 minutes)

Prior to initiation of study treatment with APR-246 administered IV in combination with venetoclax and rituximab (during treatment cycles 2-7), patients will receive APR-246 alone on Day 1 and Day 2 of the 7-day monotherapy lead-in period, during which PK and PD of APR-246 following IV and PO administration will be evaluated. On Day 1 of the monotherapy lead-in period, APR-246 will be administered IV at the assigned cohort dose. On Day 2, APR-246 will be administered PO at the dose of 500 mg. This dose may be increased based on emerging PK data to determine dose linearity after oral dosing. Patients will be required to fast for at least 10 hours prior to APR-246 PO administration. Furthermore, a sub-group of patients may receive an oral dose of APR-246 in combination with a standard high-fat meal to determine the effect of food on APR-246 absorption.

Additional dose levels may be explored if warranted based on emerging DLT, safety, PK, and/or PD data. In addition, patients who have received at least 3 cycles of therapy at the assigned dose cohort level may advance to the next higher dose level once the next higher dose level has been declared safe by the DRT.

Responses will be assessed according to response criteria for RT ([Appendix V](#)) via blood, BM, and imaging (positron emission tomography [PET]/computed tomography [CT]). Response assessments are to be performed every 3 cycles and PET-CT scanning is recommended. For patients who achieve CR, imaging may be omitted, and minimal residual disease (MRD) assessment will be completed using flow cytometry and/or molecular techniques from the BM and/or peripheral blood.

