TEAEs that meet the above criteria but that occur after the DLT evaluation period will not be defined as DLTs and will be reported as AEs/SAEs and will be reviewed across all cohorts during the study to help determine the AE profile for the respective treatment regimens under study. A patient that discontinues APR-246 therapy before completion of Cycle 3 without DLT is considered evaluable for the purpose of safety review by the DRT only if at least 75% of the scheduled doses of APR-246 were administered in Cycles 1 through 3.

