5.2 Dose Interruptions/Withholding

Study treatment, including APR-246, venetoclax, and/or rituximab, may be withheld from a patient based on the Investigator's decision in the event of intercurrent illness, AE, administrative reasons, or other reasons. If the patient's condition subsequently improves, or the situation that resulted in withholding study drug rectifies itself, the Investigator may resume dosing as soon as possible, unless the delay is more than 4 weeks. For study treatments held longer than 4 weeks, the Investigator should consult with the Medical Monitor before study treatments are resumed.

Dose management guidelines in [Table 5](#) should be followed for each occurrence of a grade ≥ 3 hematologic toxicity or those in [Table 6](#) for non-hematologic toxicity.

Table 5. Dose management guidelines for new onset hematologic toxicities

Toxicity	Occurrence	APR-246	Venetoclax	Rituximab
Grade 3 hematologic toxicity with fever and/or infection; or grade 4 hematologic toxicity	1 st occurrence • Hold all study treatments until blood count(s) return to baseline or grade ≤1 and fever and/or infection resolve if present. Treat promptly.	
 Consider reducing APR-246 by one dose level from starting dose for all future cycles of treatment if toxicity does not resolve to grade ≤1 within 7 days from onset date despite maximal medical intervention(s). If unable to reduce APR-246 dose, discuss with study Medical Monitor before resuming or discontinuing treatment. Initiate or reassess prophylaxis measures. Refer to Section 5.3.2.2 for supportive management guidelines specific to infection prophylaxis and neutropenia. 	
 Refer to Section 5.3.3.1 for venetoclax dose modification guidelines. 	
 Resume rituximab at same dose level once event resolves to baseline or grade ≤1, except in case of serious infection. For patients diagnosed with a serious grade ≥3 infection, rituximab should be permanently discontinued.

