- e. Physical exam and vital signs (including blood pressure, heart rate, respiration rate and temperature) are completed for safety purposes and clinically significant items are recorded as AEs where appropriate. Vital signs are collected prior to APR-246 infusion, 2 hours into infusion and at EOI (± 30 minutes at all time points). On Day 2 of the APR-246 monotherapy lead-in period, vital signs are collected prior to PO administration of APR-246, and then 2 hours and 6 hours after APR-246 administration. For patients with palpable lymphadenopathy and/or organomegaly, 2 dimensional measurements of lymph nodes and measurements of liver/spleen size (below costal margin) may be included as part of each physical examination as clinically indicated.
- f. Study treatment will consist of APR-246 at assigned dose level administered once weekly, on Days 1, 8 and 15 of each 28-day cycle. On Day 2 of the monotherapy lead-in period, a single dose of APR-246 will be administered PO.
- g. Venetoclax is given PO at the dose of 20 mg during Week 1, 50 mg during Week 2, 100 mg during Week 3, 200 mg during Week 4, and 400 mg during Week 5 and thereafter. Each dose should be given once daily at approximately the same time every day, with a meal and water. At the discretion of the treating Investigator, patient may be hospitalized prior to administration of the first dose of venetoclax (20 and 50 mg) and continuing for 24 hours after.
- h. Rituximab will be initiated IV, following the 5-week venetoclax dose ramp-up, at 375 mg/m^2 on Cycle 2, Day 2 ($+3$ days) and 500 mg/m^2 on Day 2 ($+3$ days) of Cycles 3-7. After 6 cycles of treatment with APR-246 + venetoclax + rituximab, APR-246 and venetoclax will continue to be administered in Cycle 8 and beyond for up to 24 cycles.
- i. Responses will be assessed every 3 cycles starting at Cycle 4 on Day 1 (± 7 days) according to Lugano response criteria via PET/CT imaging, blood, and BM. For patients who achieve CR, imaging may be omitted, and MRD assessment will be completed using flow cytometry and/or molecular techniques.
- j. Hematology must include complete blood count with differential. Hematology test should be completed before and after APR-246 administration on Days 1 and 2 of the APR-246 monotherapy lead-in period, Day 3 of the lead-in period, and on Day 1 of Cycle 1 before and approximately 4 hours after APR-246 administration.

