7.1.2.7 Safety Monitoring Plan

The Medical Monitor is responsible for ongoing safety monitoring for the study per the detailed safety plan. This monitoring will include a review of all SAEs as they are reported by the study site. The Medical Monitor will also be in contact with site monitors and will be available to discuss any issues concerning safety with site staff. Safety data will be reviewed periodically by [REDACTED] and the Sponsor Medical Officer.

The DRT consisting of the Medical Monitor, Site Principal Investigators, and other clinical research personnel that the Sponsor may deem appropriate will hold DRMs on an interim basis at a frequency dependent on study accrual. At these meetings, the DRT will review AEs and DLTs and any available PK and/or PD data and make recommendations regarding the recommended dose of APR-246. All accumulated safety data will be discussed during DRMs.

The DRT will produce summaries or minutes of these meetings. These summaries will be available for inspection when requested by any of the regulatory bodies charged with the safety of human patients and the integrity of data.

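### A met stopping criterion pauses enrollment and starts a DRT review, but no readable text holds within-patient APR-246 dose increases while that review is open

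*Combined protocol and SAP*

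**What the plan says.** **Stopping rule.** Section 8.4 lists four criteria: a death, a repeated SAE, a severe unresolved AE in more than two patients, and an unresolved grade 3 or higher neurologic AE. It then gives the consequence: "If a stopping criterion is met, enrollment will be temporarily suspended". The Statistics part of the synopsis says the same and adds when the pause ends: "enrollment will be temporarily suspended until the DRT has performed a prompt cumulative review of safety data". In both places, a change to dosing is something the DRT may decide at the end of its review. It is not a measure in force while the review runs.

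**Advance rule.** Section 4.1 says that patients with at least 3 cycles at their assigned level "may advance to the next higher dose level once the next higher dose level has been declared safe by the DRT". The Treatment Plan in the synopsis is narrower. The target must be "the next dose level of APR-246 that has been demonstrated as safe and tolerable by the DRT in at least 3 patients", and the Investigator must judge the increase to be in the patient's best interest.

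**Nearby text.** Under Section 5.2, study treatment "may be withheld from a patient based on the Investigator's decision in the event of intercurrent illness, AE, administrative reasons, or other reasons". Section 7.1.2.7 states: "The Medical Monitor is responsible for ongoing safety monitoring for the study per the detailed safety plan". That plan is not among the documents supplied.

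**The concern.** The stopping criteria mark events serious enough that the sponsor wants the DRT to look again at all the safety data before anyone new is exposed. A patient moving up a dose level is also newly exposed, to a dose that patient has not had before. It would be odd to protect the next enrollee and not the patient about to step up.

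The clearance that permits the step predates the event, and under the synopsis it may rest on as few as 3 patients. The increase is elective: postponing it leaves the patient on the current dose. Holding it during a review therefore costs the patient little, while allowing it means a larger dose is given before the body responsible for dose decisions has reached one.

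**Working it through.** The plan states no figure on this point, so there is none to reproduce. The check sets the rules side by side and then sizes the step and the pool of patients.

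**1. Does any readable rule hold an advance during a review?**

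| Place | What it does | Holds an advance during an 8.4 review? |
|---|---|---|
| 8.4 and synopsis, Statistics | Pauses enrollment; DRT reviews | No; only enrollment is named |
| 4.1 and synopsis, Treatment Plan (advance) | Allows an advance on DRT clearance | No; review status is not mentioned |
| 4.1 (two or more DLTs at Dose Level 1) | Pauses enrollment; DRT considers dose or schedule changes | No; also names only enrollment |
| 5.2 and Tables 5 and 6 | Investigator may withhold; tables respond to the patient's own toxicity | No; an event in another patient triggers nothing |
| 4.5 | Sponsor may terminate the study | No; discretionary, and about the whole study |
| 7.1.2.7 | Medical Monitor oversight and DRT meetings | No hold stated; defers to a plan not supplied |
| 5.1.1 | Redacted | Unknown |

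**2. Size of the step** (dose levels from Section 4.1, Table 3).

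- Level 1 to 2: 3.0/1.5 − 1 = 100%.
- Level 2 to 3: 4.0/3.0 − 1 = 33%.

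**3. Earliest eligibility** (cycle lengths from Section 4.1). Lead-in plus Cycles 1 to 3: 7 + 35 + 28 + 28 = 98 days from first dose.

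**4. When the next level could be cleared.** Assume that clearing a level needs the full DLT period and that cohorts follow without a gap. Section 4.1 runs that period to the end of Cycle 3, which is 98 days; Section 5.1.4 states 91 days. A patient in the first Level 1 cohort must wait for Level 1 to finish and then for Level 2 to finish: at least 91 + 91 = 182 days, or 98 + 98 = 196 days. Section 2.1 gives median survival in this disease as 3 to 11 months, so many such patients will not be on treatment by then. Patients added later at Dose Levels 1 and 2 (Section 8.1) could qualify from about day 98, because the next level would already be cleared. The pool is small but not empty.

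**5. Could a review plausibly open?** As an illustration only, take one type of SAE not attributed to disease, with an assumed per-patient rate p. The criterion needs more than one patient, so the chance among n patients is 1 − (1 − p)^n − np(1 − p)^(n−1). For n = 18 this is 0.23, 0.55 and 0.90 at p = 5%, 10% and 20%. These rates are assumptions. The result says that a review is not a remote event; it does not say how often one would coincide with a planned advance.

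**The case against.** The best case against the point is that it reads silence as permission. The advance is optional and depends on the DRT's view that the level is safe. The DRT conducting the review is the same body that gave the clearance, and the Medical Monitor and site principal investigators sit on it. SAEs must be reported within 24 hours. The synopsis is part of the protocol, so its best-interest condition applies even though Section 4.1 omits it. Nothing says that a clearance survives an open review. All of this stands, and it makes an advance during a review unlikely. It does not forbid one: no readable text suspends the clearance, and protection rests on individual judgment where enrollment has an automatic rule.

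The second objection is that absence is not shown, because Section 5.1.1 is redacted and the safety plan was not supplied. That also stands and limits the finding to the readable text.

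A reader might infer more in three ways that the documents do not support.

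- *That all four criteria run to 30 days after last dose, so the rule is empty once accrual closes.* Only the death criterion carries that window. After accrual closes, a met criterion still triggers the DRT review, which can change dosing.
- *That the DLT rules make the gap worse, since* "TEAEs that meet the above criteria but that occur after the DLT evaluation period will not be defined as DLTs". Such events are still reviewed across cohorts, and a toxicity inside the DLT period does not expressly freeze advances either. The DLT period does not bear on this point.
- *That the frequency can be read from the calendar*, because APR-246 is "administered once weekly, on Days 1, 8 and 15 of each 28-day cycle". A weekly infusion falling within a review shows only that dosing continues. The plan does not state the length of a review, and a patient cleared earlier may already have advanced.

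**Conclusion.** The point holds for the readable text. A met Section 8.4 criterion suspends enrollment and triggers a prompt DRT review, but it does not hold a within-patient advance on an earlier DRT clearance. Followed exactly, the rules allow an elective increase of 100% or 33% before the DRT decides whether dosing should change.

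The importance is low to moderate. Few patients are likely to be eligible when a review opens, discretion will usually prevent the step, and no endpoint, sample size or analysis is affected. How often it would happen cannot be estimated from the documents. The conclusion assumes that neither redacted Section 5.1.1 nor the safety plan contains a hold. It is a gap in a safety rule, and it should not be read as a statement that the protocol endorses raising doses during a review.

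**What to change.** Four short edits by amendment.

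- In Section 8.4 and in the stopping text of the synopsis, state: *Enrollment and all within-patient APR-246 dose increases are suspended until the DRT has completed its review.*
- In the advance rule in Section 4.1 and in the synopsis Treatment Plan, add: *No advance is permitted while a review under Section 8.4 is open.*

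If Section 5.1.1 or the safety plan already contains this hold, a cross-reference from Section 8.4 is enough.

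No new committee, visit or data item is needed. The downside is that an optional dose increase waits for the length of the review. The plan calls the review prompt but sets no time limit, so the delay cannot be given in days.
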